12.2.8 Percentage of Subjects with a new Symptom

The eighth secondary efficacy endpoint is the percentage of subjects with a new symptom (compared to baseline) on the NTM Symptom Assessment Questionnaire with severity worse than mild at the Day 28, 56, and 84 visit, and Day 84/EOT.

For a symptom to be considered new it must be absent at baseline and graded with a severity worse than mild at the post-baseline assessment

The number and percentage of subjects with a new symptom worse than mild, with a new symptom that is not worse than mild, and no new symptom will be presented at each time point.

A shift table will also be provided for the shift from baseline severity to each post-baseline time point severity for each symptom.

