4 STUDY OBJECTIVES AND ENDPOINTS

Objective	Endpoint
Primary	
Efficacy: To evaluate the efficacy of omadacycline in adult subjects with NTM pulmonary disease caused by MABC based upon subject assessment of symptoms	
Including but not limited to:
 
• Clinical response at Day 84 defined as improvement in severity of at least 50% of the symptoms present at baseline• Clinical response at Day 84 defined as improvement in severity of at least 50% of the symptoms present at baseline and no deterioration in severity of symptoms present at baseline
Safety: To evaluate the safety and tolerability of omadacycline in adult subjects with NTM pulmonary disease caused by MABC	
• Incidence of adverse events (AEs) and serious adverse events (SAEs)• Change from baseline for:
o Clinical laboratory parameterso Vital signso Electrocardiograms (ECGs)• Incidence of potentially clinically significant:
o Clinical laboratory parameterso Vital signso ECGs

[figure not shown]
Secondary	
To evaluate patient-reported outcomes (PROs) and quality of life in adult subjects with NTM pulmonary disease caused by MABC	
• Quality of Life – Bronchiectasis (QOL-B)• St. Georges Respiratory Questionnaire (SGRQ)• Patient-Reported Outcomes Measurement Information System Short Form v1.0 – Fatigue 7a Daily (PROMIS Short Form v1.0 – Fatigue 7a Daily)• Patient Global Impression of Change (PGI-C)• Patient Global Impression of Severity (PGI-S)• Clinical Global Impression – Severity of Illness (CGI-S)• Clinical Global Impression – Global Improvement Scale (CGI-I)• No new symptom (ie, symptom not present at baseline) with severity worse than mild
To evaluate the microbiological response of omadacycline in adult subjects with NTM pulmonary disease caused by MABC	
• Decrease in quantitative sputum culture at Day 84• Time to growth in liquid medium only• Time to first negative sputum culture

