8.12 NTM Symptom Assessment Questionnaire

The NTM Symptom Assessment Questionnaire is a tool created by Paratek to evaluate efficacy based on individual subject assessment of symptoms. It is a self-administered questionnaire that evaluates a list of 12 common NTM symptoms, asking subjects if they have experienced each symptom within the past 7 days. Responses are provided using a 4-point scale (absent, mild, moderate, severe) and should reflect the subject's perceived overall impression of their symptoms over the past 7 days. This questionnaire is completed by the subject without interpretation of the subject's response by a clinician or site staff.

In addition, at Screening, subjects will be asked to list up to 3 of their most bothersome symptoms.

The NTM Symptom Assessment Questionnaire will be completed at Screening, Baseline/Day 1 (prior to first dose of test article), and the Day 28, Day 56, and Day 84/EOT Visits. Responses at Screening and Baseline/Day 1 will be used to determine eligibility.

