For the PGI-C, the number and percentage of subjects with each response will be presented by visit and treatment group. The PGI-C will also be categorized as improved vs. no change/worse and the number and percentage of subjects in each category will be presented by visit and treatment group. Exact 2-sided 95% CIs using the Clopper-Pearson method for the percent improved and a p-value from Fisher's exact test will be provided.

Descriptive statistics for severity of illness from the CGI change from baseline for each visit will be presented by treatment group. Descriptive statistics of the global improvement and the efficacy index from the CGI will also be provided by treatment group for each visit. A p-value from the Wilcoxon rank sum test for each outcome will also be presented.

At each visit based on the NTM Symptom Assessment Questionnaire, the number and percentage of subjects with a new symptom (compared with baseline) with severity worse than mild and no new symptoms with a severity worse than mild will be summarized by treatment group. Shift tables from baseline for each symptom at each visit will also be provided.

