5. DETERMINATION OF SAMPLE SIZE

As the study is exploratory with respect to determination of efficacy, the sample size determination is provided to better ensure sufficient subjects are enrolled to provide an initial assessment of efficacy rather than test a specific hypothesis. With a randomization ratio of 1.5:1, a sample size of 75 subjects (45 omadacycline and 30 placebo) will provide approximately 80% power to detect an absolute treatment difference of 30% in clinical response rate at Day 84, based on clinical response rates of 15% and 45% in the placebo and omadacycline treatment groups respectively, using a Mantel-Haenszel test with 2-sided alpha level of .05.

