11.1 Efficacy Variables

The primary efficacy endpoints are:

- Clinical response (Definition 1) is defined as improvement at the Day 84 visit in severity of at least 50% of symptoms on the NTM Symptom Assessment Questionnaire present at baseline.

- Clinical response (Definition 2): is defined as improvement at the Day 84 visit in severity of at least 50% of symptoms on the NTM Symptom Assessment Questionnaire present at baseline and no deterioration in severity of any symptoms present at baseline.

Supportive analyses include analysis of clinical response (Definition 1 and Definition 2) at the Day 28 and Day 56 visits.

The secondary efficacy endpoints are:

- Change from baseline in Quality of Life - Bronchiectasis (QOL-B) domain scores at days 28, 56, 84, and Day 84/EOT
- Change from baseline in the St George's Respiratory Questionnaire (SGRQ) global and component scores at days 28, 56, 84, and Day 84/EOT
- Change from baseline in the Patient-reported Outcomes Measurement Information System (PROMIS) Fatigue 7a Short Form standardized score at days 28, 56, 84, and Day 84/EOT
- The Patient Global Impression – Change (PGI-C) response at days 28, 56, 84, and Day 84/EOT
- The Patient Global Impression – Severity (PGI-S) response at days 28, 56, 84, and Day 84/EOT
- The Clinical Global Impression – Improvement (CGI-I) response at days 28, 56, 84, and Day 84/EOT
- The Clinical Global Impression – Severity (CGI-S) response at days 28, 56, 84, and Day 84/EOT
- The percentage of subjects with a new symptom (defined as a symptom present post-baseline but absent at baseline) on the NTM Symptom Assessment Questionnaire with severity worse than mild at days 28, 56, 84, and Day 84/EOT
- The percentage of subjects with a decrease in quantitative MABC sputum culture from baseline to Day 84
- Time to growth in liquid medium only
- Time to first sputum culture negative for MABC

The additional efficacy endpoints are:

- Time to detection of MABC in growth media at baseline and the Day 28, 56, 84 and Day 84/EOT visits
- The percentage of subjects who convert from a positive MABC sputum culture at baseline to a sputum culture negative for MABC at any time post-baseline and at the Day 28, 56, 84 and Day 84/EOT visits
- In those subjects whose first negative culture (i.e., convert from a positive MABC sputum culture at baseline to a negative MABC sputum culture) is on the Day 28, 56, 84 and Day

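### SAP 12.2.8 counts a symptom as new only if it is worse than mild, so its own row for new symptoms that are not worse than mild can only be zero if programmed as written

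*SAP*

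**What the plan says.** The NTM Symptom Assessment Questionnaire lists 12 symptoms. Protocol section 8.12: "Responses are provided using a 4-point scale (absent, mild, moderate, severe").

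Protocol section 4 lists as a secondary endpoint: "No new symptom (ie, symptom not present at baseline) with severity worse than mild". Newness is explained in the parenthesis, and severity is a further condition. Protocol section 12.5.2.1 plans two categories per visit: subjects "with a new symptom (compared with baseline) with severity worse than mild and no new symptoms with a severity worse than mild".

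SAP section 11.1 keeps the same structure. The endpoint is the percentage of subjects with "a new symptom (defined as a symptom present post-baseline but absent at baseline") whose severity is worse than mild.

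SAP section 12.2.8 moves severity into the definition itself: "For a symptom to be considered new it must be absent at baseline and graded with a severity worse than mild at the post-baseline assessment". It then plans a three-row summary, in which the first row is a new symptom worse than mild and the others are subjects "with a new symptom that is not worse than mild, and no new symptom will be presented at each time point". It ends with a further output: "A shift table will also be provided for the shift from baseline severity to each post-baseline time point severity for each symptom".

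SAP section 14 declares no changes from the protocol-specified analyses.

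**The concern.** Two consecutive statements in 12.2.8 cannot both be followed with any effect. If a symptom must be worse than mild to be new, no symptom is both new and not worse than mild, and the middle row is empty whatever the data. A subject who had no fatigue or appetite loss at baseline and reports both as mild at Day 84 would be counted under no new symptom, which is untrue of that subject.

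At stake is a descriptive split, but one with a purpose. SAP section 12.1.1 leaves symptoms absent at baseline out of both primary response definitions, so 12.2.8 is the planned subject-level summary of symptoms that emerge on treatment on this questionnaire. Under the table conventions in SAP Appendix A, a category with no subjects is still displayed, as a count of 0 without a percentage. A reader of the report could take that zero for an observation.

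The double programming in SAP Appendix B would not reliably catch the fault. Two programmers who both follow 12.2.8 agree on an empty row. If one follows 11.1 they disagree, and the SAP does not say which section governs.

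**Working it through.** **The plan's own figures.** Section 12.2.8 states none. The SAP's only power figure (section 5: "a sample size of 75 subjects (45 omadacycline and 30 placebo) will provide approximately 80% power") concerns clinical response and plays no part here. For completeness it reproduces. With rates 0.15 and 0.45, the pooled rate is (30 × 0.15 + 45 × 0.45)/75 = 0.33. The pooled standard error is √(0.33 × 0.67 × (1/30 + 1/45)) = 0.1108, and the unpooled one is √(0.15 × 0.85/30 + 0.45 × 0.55/45) = 0.0987. Power = Φ((0.30 − 1.96 × 0.1108)/0.0987) = Φ(0.84), about 79.9%. Exact enumeration of the unstratified Mantel-Haenszel test gives 80.2%.

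**Inputs for the check.** Four severity levels (protocol 8.12), the definition in SAP 12.2.8, the definition in SAP 11.1, and the three rows in SAP 12.2.8. Each subject is placed by the worst new symptom, and answers are taken as complete.

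**Step 1: one symptom.** There are 4 × 4 = 16 pairs of baseline and post-baseline severity. Four start from absent:

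| Baseline → visit | Row under 12.2.8 | Row under 11.1 |
|---|---|---|
| absent → absent | no new symptom | no new symptom |
| absent → mild | **no new symptom** | **new, not worse than mild** |
| absent → moderate | new, worse than mild | new, worse than mild |
| absent → severe | new, worse than mild | new, worse than mild |

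The other 12 pairs start from a symptom already present and are not new under either definition. The definitions differ in one pair only, absent to mild.

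**Step 2: k symptoms.** There are 16^k patterns. A symptom avoids being new and worse than mild in 14 of its 16 pairs, and avoids being new at any severity in 13. Hence:

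- Worse-than-mild row, both definitions: 16^k − 14^k
- Middle row: 0 under 12.2.8; 14^k − 13^k under 11.1
- No-new-symptom row: 14^k under 12.2.8; 13^k under 11.1

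| k | All patterns | Worse than mild (both) | Middle row, 12.2.8 | Middle row, 11.1 | No new, 12.2.8 | No new, 11.1 |
|---|---|---|---|---|---|---|
| 1 | 16 | 2 | 0 | 1 | 14 | 13 |
| 2 | 256 | 60 | 0 | 27 | 196 | 169 |
| 3 | 4096 | 1352 | 0 | 547 | 2744 | 2197 |

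Full enumeration for k = 1, 2 and 3 gives the same counts. These are counts of possible answer patterns, not expected numbers of patients.

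**Step 3: what moves.** With three symptoms, 2744 − 2197 = 547 patterns leave the no-new-symptom row under 11.1, and all 547 go to the middle row. None enters or leaves the worse-than-mild row.

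**Step 4: can the shift table replace the row?** It counts absent-to-mild moves one symptom at a time. One subject with new mild fatigue and new mild poor appetite adds one to each of two symptoms. Two subjects with one such symptom each produce the same entries. The shift table therefore does not determine how many subjects had any new mild symptom, nor how many of them had nothing worse.

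**The case against.** The strongest case on the other side is that nothing of consequence changes.

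- *A reader might infer that the eighth secondary endpoint is wrong.* It is not. Its numerator, subjects with a new symptom worse than mild, is identical under both definitions. This objection stands.
- *A reader might infer a departure from the protocol's analysis.* Under the literal 12.2.8 rule, the first and last rows are exactly the protocol's two categories in section 12.5.2.1. The middle row is an SAP addition. This also stands; the fault is in how the remaining subjects are split and labelled.
- *A reader might infer that mild emerging symptoms go unreported.* The shift table shows them by symptom and visit, and SAP section 6 has summary tables presented by treatment group. What it cannot supply is the count of subjects, so this objection stands in part.
- *A reader might infer that the report will certainly show the zero.* The three-row instruction makes sense only if new includes mild, and a programmer may well follow 11.1. The table mocks are in a separate document (SAP Appendix C) and are not available here. The consequence is therefore conditional on literal programming.
- *A reader might infer that everyone with a new mild symptom is misfiled.* A subject who also has a new moderate or severe symptom is correctly placed in the first row. Only those whose new symptoms are all mild are affected.

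None of this removes the contradiction between the definition and the row requested directly below it.

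**Conclusion.** The point holds as a minor error of wording with a definite effect on one table. SAP 12.2.8 conflicts with SAP 11.1, with protocol section 4 and with its own three-row layout. If its sentence is programmed as written, the middle row is a structural zero count in both arms at every visit, and subjects whose new symptoms are all mild are counted as having none.

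The size in patients cannot be given, because the documents state no incidence of new symptoms and any percentage would rest on invented inputs. The conclusion rests only on the wording and the four-level scale. No test or p-value is attached to this endpoint in 12.2.8, efficacy is declared exploratory, and no sample size, power or alpha figure is touched.

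**What to change.** In SAP 12.2.8, replace the sentence defining a new symptom with the 11.1 definition: absent at baseline and mild, moderate or severe at the post-baseline visit. Add that each subject is classified once per visit by the worst new symptom: worse than mild, mild only, or none.

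The three rows are then mutually exclusive and cover every subject with a completed questionnaire at that visit. Adding the last two together returns the protocol's second category, so nothing already planned is lost.

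The cost is one replaced sentence and one added sentence, with no new data or tests. If the table has already been produced, check which definition was programmed, rerun that table if needed, and record the clarification in the clinical study report, where SAP section 1 places deviations from the plan.

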12.2.9 Percentage of Subjects with a Decrease in Quantitative Mycobacterial Sputum

The ninth secondary efficacy endpoint is the percentage of subjects with a decrease in quantitative mycobacterial load from the sputum culture collected at the Day 84 visit and defined as a reduction in the semi-quantitative score (as defined in Table 10.3.2) as compared to baseline. The number and percentage of subjects with a reduction in the semi-quantitative score at the Day 84 visit will be presented for the ITT analysis set by treatment group. Exact 2-sided 95% CIs for the point estimate of the percentage of subjects with a decrease in each treatment group will be determined using the Clopper-Pearson method. The odds ratio (omadacycline relative to placebo) and p-value will be calculated using Cochran-Mantel-Haenszel test, stratified by prior antibiotic use. If the sample size is too small in one of the randomization stratification subgroups such that an adjusted analysis cannot be performed, an unadjusted analysis (chi-squared or Fisher's exact test) will be used.

12.2.10 Time to Growth in Liquid Medium Only

Kaplan-Meier methods will be utilized to determine the time to growth in liquid medium only for MABC for the ITT Analysis Set by treatment group. The analysis will be limited to subjects with growth on agar plate at baseline in the ITT Analysis Set. Time to growth in liquid medium only will be defined as the number of days from the date of test article administration to the date of the first assessment where growth is detected in liquid medium only. If there is no sputum sample indicating growth in liquid medium only but there is a negative culture (defined in Section 12.2.11), the date of the first negative culture will be used for the determination of time to growth in liquid medium only.

Subjects who died, withdrew from the study, or received alternative antibiotic therapy (not including chronic macrolides) for treatment of the NTM infection prior to growth in liquid medium only for MABC (or a negative culture, if no sputum sample indicating growth in liquid medium only) will be censored at the date of the death, study withdrawal, or the start date of the alternative antibiotic therapy respectively. Subjects who have a positive sputum culture (defined as growth in both liquid medium and agar plate [growth on both LJ slant and biplate]) through Day 84 will be censored at the date of the Day 84 visit.

The median, 25th and 75th percentile for time to growth in liquid medium only will be provided with 2-sided 95% CIs for each treatment group. A p-value will be determined using a stratified (by prior antibiotic use) log-rank test. Kaplan-Meier curve for time to growth in liquid medium only will be provided in a figure.

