12.5.2.2 Microbiological Response

The number and percentage of subjects with a decrease in the mycobacterial load will be determined by treatment group at Day 84 in the ITT Analysis Set. Exact 2-sided 95% CIs for the point estimate of the percentage of subjects of subjects with a decrease in mycobacterial load in each treatment group will be determined using the Clopper-Pearson method. The odds ratio (omadacycline relative to placebo) and p-value will be calculated using Cochran-Mantel-Haenszel test, stratified by prior antibiotic use.

Kaplan-Meier methods will be utilized to determine the time to growth in liquid media only and time to first negative sputum culture in the ITT Analysis Set. Time to growth in liquid medium only will be defined as the number of days from the date of test article administration to the date of the first assessment where growth is detected in liquid medium only. Time to first negative sputum culture is defined as the number of days from the date of test article administration to the date of the first negative sputum culture. Subjects who died, withdrew, or took alternative antibiotic therapy for treatment of the NTM infection prior to growth in liquid medium only or negative sputum will be censored at the date of the death, study withdrawal, or the start date of the alternative antibiotic therapy respectively. The median, 25th and 75th percentile for time to growth in liquid media and time to first negative sputum culture will be provided with 2-sided 95% CIs. A p-value will be determined using a log-rank test.

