10.2.2 Baseline Analyses

The following will be provided for the baseline MABC specimen:

- Baseline positive culture for MABC and by subspecies, as well as MAC and other mycobacterium.
- Distribution of the semi-quantitative score defined as follows:

Semi-quantitative culture scores	Growth in broth	Growth on agar plate	CFU/mL on an agar plate
0	-	-	0
1	+	-	0
2	+/-	+	1 - <50
3	+/-	+	50-99
4	+/-	+	100-199
5	+/-	+	200-299
6	+/-	+	≥300

- Distribution of MIC to amikacin, cefoxitin, ciprofloxacin, clarithromycin, clarithromycin-D14, clofazimine, doxycycline, imipenem, linezolid, minocycline, moxifloxacin, omadacycline, tigecycline, and trimethoprim/sulfamethoxazole
- Susceptibility profile (interpreted as resistant, susceptible and intermediate according to CLSI breakpoints) to each antibiotic with defined breakpoints
- Multidrug Resistance (MDR) defined as nonsusceptibility (MIC value interpreted as “I” or “R”) to at least one agent in three or more antimicrobial categories. Agents that do not have susceptibility interpretations i.e. those in Table 10.3.2 with ‘N/A’ will not be considered in this analysis.
- MIC range, MIC₅₀ and MIC₉₀ to omadacycline

Table 10.3.2. Antimicrobial Categories, Agents and CLSI Breakpoints

Antimicrobial Category for MDR evaluation	Antimicrobial Agent	MIC ug/mL		
		S	I	R
Aminoglycoside	Amikacin	≤16	32	≥64
Cephalosporin	Cefoxitin	≤16	32-64	≥128
Fluoroquinolone	Ciprofloxacin	≤1	2	≥4
Macrolide	Clarithromycin	≤2	4	≥8
N/A	Clofazimine	N/A	N/A	N/A
Tetracycline	Doxycycline	≤1	2-4	≥8
Carbapenem	Imipenem	≤4	8-16	≥32
Oxazolidinone	Linezolid	≤8	16	≥32

N/A	Minocycline	N/A	N/A	N/A
Fluoroquinolone	Moxifloxacin	≤1	2	≥4
Antifolate	Trimethoprim-sulfamethoxazole	≤2/38		≥4/76
N/A	Tigecycline	N/A	N/A	N/A

S=Susceptible, I=Intermediate, R=Resistant

Clinical and Laboratory Standards Institute. Performance Standards for Susceptibility Testing of Mycobacteria, Nocardia spp., and Other Aerobic Actinomycetes 1st ed. CLSI document M62. 2018. CLSI, [name].

Microbiology results will be incorporated into several of the efficacy analyses, as defined in Section 11.1.

The by-subject listings noted below will also be provided. On each listing, all samples will be presented and the baseline and post-baseline samples selected as indicated above will be indicated with a flag.

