12.2.11 Time to First Negative Sputum Culture

Kaplan-Meier methods will be utilized to determine the time to first sputum culture negative for MABC for the ITT Analysis Set by treatment group. Time to first negative sputum culture is defined as the number of days from the date of the first dose of test article administration to the date of the first sputum culture negative for MABC. A culture is considered negative if there is no growth in broth (ie, liquid medium) and no growth on agar plate (ie, no growth on either LJ slant or biplate) for MABC regardless of subspecies. For example, if the baseline culture grows *M. abcessus* subspecies *abcessus* and the post-baseline sample grows *M. abcessus* subspecies *massiliense*, the culture is considered positive for MABC. Subjects who died, withdrew from the study, or received alternative antibiotic therapy (not including chronic macrolides) for treatment of the NTM infection prior to sputum culture negative for MABC will be censored at the date of the death, study withdrawal, or the start date of the alternative antibiotic therapy respectively. Subjects who have a positive sputum culture through Day 84 will be censored at the date of the Day 84 visit.

The median, 25th and 75th percentile for time to first negative sputum culture will be provided with 2-sided 95% CIs for each treatment group. The probability of a negative sputum culture at Days 28, 56 and 84 will also be presented along with the 2-sided 95% CIs for each treatment group. A p-value will be determined using a stratified (by prior antibiotic use) log-rank test. Kaplan-Meier curve for time to first negative sputum culture will be provided in a figure.

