12.3 Additional Efficacy Analyses

- Time to detection of MABC (in days) in liquid growth medium at baseline and the Day 28, 56, 84 and Day 84/EOT visits will be summarized by treatment group, including n, mean, SDs, median, minimum and maximum.
- The number and percentage of subjects who convert from a positive MABC sputum culture at baseline to a sputum culture negative for MABC at any time post-baseline and at the Day 28, 56, 84 and Day 84/EOT visits and who do not convert to a negative culture (i.e., remain positive) will be summarized by treatment group.
- In those subjects whose first negative culture (i.e., convert from a positive MABC culture at baseline to a negative MABC culture) is on the Day 28, 56, 84 and Day 84/EOT visits, the number and percentage of subjects with a culture positive for *M. avium* or other non-abscessus mycobacterium species at baseline and at the visit will be summarized by treatment group.
- The number and percentage of subjects who convert from a positive MABC culture at baseline to a sputum culture negative for MABC by the Day 56 visit and have no subsequent positive MABC culture will be presented, as well as the number and percentage of subjects who convert to a negative culture by the Day 56 visit and have a subsequent positive culture, and those who do not convert to a negative culture by Day 56 will be summarized by treatment group.
- The number and percentage of subjects who convert from a positive MABC sputum culture at baseline to a sputum culture negative for MABC or growth of MABC only in liquid medium at any time post-baseline and at the Day 28, 56, 84 and Day 84/EOT visits and who do not convert to a negative culture will be summarized by treatment group.
- The number and percentage of subjects whose first negative culture (i.e., convert from a positive MABC culture at baseline to a negative MABC culture) is on the Day 28, 56, 84 and Day 84/EOT visits will be summarized by treatment group.
- A shift table of the semi-quantitative score from baseline to Days 28, 56, 84 and EOT visits will be presented by treatment group.
- Quantitative mycobacterial load (CFU/mL) and semi-quantitative score of the MABC at baseline and the Day 28, 56, 84 and Day 84/EOT visits will be summarized by treatment group, including including n, mean, SDs, median, minimum, and maximum, geometric mean, 95% CI of geometric mean, and %CV for mycobacterial load and number and percentage of subject of each semi-quantitative score.

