14. CHANGES TO PROTOCOL-SPECIFIED ANALYSES

There are no changes from the protocol specified analyses.

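### Time to growth in liquid medium only: a later liquid-only culture overrides an earlier negative one, so event date and status depend on samples not yet taken

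*SAP*

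**What the plan says.** SAP 12.2.10 restricts the analysis to ITT subjects with agar growth at baseline and runs event time from test article administration "to the date of the first assessment where growth is detected in liquid medium only". It then adds a substitute event. The condition is "If there is no sputum sample indicating growth in liquid medium only but there is a negative culture", and in that case the first negative culture supplies the date. The censoring sentence for death, withdrawal or alternative antibiotic carries the same condition in brackets: "or a negative culture, if no sputum sample indicating growth in liquid medium only". Neither sentence limits the condition to samples taken before the negative culture, and neither says that the earlier of the two results counts.

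Four other places bear on this:

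- SAP 10.2.2, under "Distribution of the semi-quantitative score defined as follows", gives score 0 to no growth in broth or on agar, score 1 to broth growth only, and scores 2 to 6 to agar growth.
- SAP 12.2.11 states "A culture is considered negative if there is no growth in broth" and none on agar, and dates its event at the first such culture.
- SAP 12.3 has a combined conversion measure: negative for MABC "or growth of MABC only in liquid medium at any time post-baseline".
- Protocol 12.5.2.2 ends event time at the "date of the first assessment where growth is detected in liquid medium only", with no negative-culture substitute. SAP Section 14 nevertheless says "There are no changes from the protocol specified analyses".

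**The concern.** In subjects who start with agar growth, a negative culture is a larger improvement than a liquid-only one. The SAP accepts it as an event, but withdraws that event if the same subject later shows growth in broth. Whether a subject has an event at Day 28 is then settled by what grows at Day 56 or Day 84. A Kaplan-Meier estimate or log-rank test at a given time should use only information available by that time.

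The ordering it produces is hard to defend. A subject negative at Day 28 who then regrows on agar at both later visits keeps the Day 28 date. A subject negative at Days 28 and 56 who regrows only in broth at Day 84 is moved to Day 84. For that second subject, SAP 12.2.11 gives Day 28 for the stronger milestone (negative culture) while 12.2.10 gives Day 84 for the weaker one.

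At stake are the curves, the reported percentiles and the log-rank p-value for this secondary endpoint. The substitution is also an undisclosed departure from the protocol, however it is read.

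**Working it through.** **Plan's own figure.** The documents give no design figure for this endpoint. The only one is about 80% power for the primary endpoint (45 vs 30 subjects, 45% vs 15%, two-sided 0.05). It reproduces with the pooled normal approximation. The pooled rate is (45 × 0.45 + 30 × 0.15)/75 = 0.33. The null SE is √(0.33 × 0.67 × (1/45 + 1/30)) = 0.1108 and the alternative SE is √(0.15 × 0.85/30 + 0.45 × 0.55/45) = 0.0987. Then z = (0.30 − 1.96 × 0.1108)/0.0987 = 0.84, so power is 79.9%. Nothing below depends on it.

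**Enumeration.** Code each post-baseline culture (Days 28, 56, 84) as N (negative), L (liquid-only) or P (agar growth), giving 3³ = 27 patterns.

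- As written: date of the first L if there is any L; otherwise the first N; otherwise censored.
- Earliest-of rule: date of the first L or N.

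The two rules differ in six patterns:

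| Pattern | As written | Earliest-of | Delay (days) |
|---|---|---|---|
| N-L-N, N-L-L, N-L-P | 56 | 28 | 28 |
| P-N-L | 84 | 56 | 28 |
| N-N-L, N-P-L | 84 | 28 | 56 |

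With the visit windows (25–31, 53–59, 82–89), the 28-day delay can be 22 to 36 days and the 56-day delay 51 to 64 days. Without censoring for death, withdrawal or antibiotics, all six remain events by Day 84 and only the timing moves.

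**Status.** A subject is negative at Day 28, starts an alternative antibiotic on Day 40 and is liquid-only at a later or EOT sample. Read literally, a liquid-only sample exists, so the negative culture does not count. The antibiotic came before the liquid-only growth, so the subject is censored at Day 40. Remove that last sample and the same subject is an event at Day 28.

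**Illustrated size.** All rates here are assumptions. Let n and l be the per-visit probabilities of N and L, with independent visits and a = 1 − n − l.

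P(affected) = n·l + [(1 − l)² − a²]·l

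| n, l | Calculation | Affected |
|---|---|---|
| 0.10, 0.05 | 0.0050 + 0.0090 | 1.4% |
| 0.25, 0.05 | 0.0125 + 0.0206 | 3.3% |
| 0.10, 0.15 | 0.0150 + 0.0240 | 3.9% |
| 0.25, 0.15 | 0.0375 + 0.0544 | 9.2% |
| 0.40, 0.20 | 0.0800 + 0.0960 | 17.6% |

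Cumulative event probability as written is l + n(1 − l)² at Day 28 and 1 − a² − [(1 − l)² − a²]·l at Day 56. Under the earliest-of rule it is 1 − a and 1 − a². Both give 1 − a³ at Day 84.

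- (0.25, 0.15): 33.1/58.6/78.4% as written, 40.0/64.0/78.4% earliest-of. No expected quartile moves.
- (0.40, 0.20): 45.6/74.4/93.6% as written, 60.0/84.0/93.6% earliest-of. The expected median moves from Day 56 to Day 28.
- (0.25, 0.05): Day 56 is 48.9% as written and 51.0% earliest-of. The expected median moves from Day 84 to Day 56.

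**Log-rank test.** Unstratified, 45:30, all subjects analysed, no dropout, 12,000 simulated trials:

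- (0.25, 0.15) vs (0.10, 0.15): rejection 46.2% as written, 50.6% earliest-of.
- (0.25, 0.05) vs (0.10, 0.15): 11.4% and 11.1%. Here placebo is affected slightly more often (3.9% vs 3.3%).

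A second model lets 30–50% of negatives regrow at the next visit. Negative probabilities are 0.20–0.25 vs 0.08 and liquid-only 0.10–0.15 vs 0.08, with 1,500 trials per setting. It dates 9–16% of omadacycline and 4–6% of placebo subjects late, with power of 76–79% as written and 80–82% earliest-of.

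**The case against.** The strongest reply is that late is measured against an endpoint the protocol does not define. For N-L-L, Day 56 is the first liquid-only assessment, exactly as Protocol 12.5.2.2 asks, and the earliest-of rule is a different, pooled endpoint. This would carry weight if the SAP had kept the protocol definition. It did not: it already treats a negative culture as an event, but makes that depend on future samples.

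The authors may also have meant no *earlier* liquid-only sample. That is possible, but the text does not say so, and the unrestricted wording appears twice. If that was the intent, the fix only records it.

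Several limits stand:

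- Six of 27 is a count of patterns, not a frequency. Independence between visits is a strong assumption. With an assumed 50% chance that a visit repeats the previous state, the affected share falls to 0.6% at (0.10, 0.05), 4.2% at (0.25, 0.15) and 8.4% at (0.40, 0.20). The median shift at (0.40, 0.20) then disappears (Day 28: 52.4% vs 60.0%), while a marginal one appears at (0.25, 0.15) (Day 56: 49.7% vs 52.0%).
- The simulations use all 75 subjects, although the analysis is limited to those with agar growth at baseline.
- The status change is a narrow case. Test article stops when alternative therapy is needed, so it would usually require an EOT sample taken after the antibiotic began.
- N-P-P is dated Day 28 under both rules. Disagreement with 12.2.11 or 12.3 is not a defect in itself, since those are separate endpoints.
- Protocol 8.10 counts inability to produce sputum after baseline as a negative culture, so an N may be no specimen at all. That weakness affects both rules and 12.2.11 alike.
- SAP 12.3 already reports the pooled measure by visit, so part of the information is visible elsewhere.

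**Conclusion.** The concern holds on the text. Six result patterns are dated 28 or 56 days late relative to the first qualifying culture. When an alternative antibiotic intervenes, event status can also turn on a later sample. The rule ranks a later, worse result above an earlier, better one by the SAP's own score.

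The enumeration needs no assumptions. The size does: across the assumed rates the affected share runs from 0.6% to 17.6%, the log-rank rejection rate changes by between almost nothing and about 5 points, and a reported median can move by a whole visit. In the regrowth model the delay falls mainly on the arm that clears more often and dilutes a real difference, but another scenario affects placebo slightly more. Direction and size by arm cannot be determined from the documents.

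The consequence is confined to one secondary endpoint in an exploratory study with nominal p-values. The primary analysis and sample size are unaffected. It should be corrected, but it does not threaten the trial's main result.

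**What to change.** In SAP 12.2.10:

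1. Define the event as the first post-baseline culture that is either liquid-only or negative for MABC, whichever is earlier.
2. Use that same event in the death, withdrawal and alternative-antibiotic censoring sentence, so that only subjects who have not yet reached it are censored.
3. As a clarification only, state that a subject with growth on any solid medium at every visit is censored at the Day 84 visit.

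In SAP Section 14, list the difference from Protocol 12.5.2.2. That entry is needed even if the present rule is kept.

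The cost is three sentences, one Section 14 entry and a small programming change. The price in principle is a further step from the protocol definition, which counts liquid-only growth alone; hence the disclosure. The change should be made before unblinding. If the blind has already been broken, the corrected analysis should be labelled post hoc, as SAP Section 6 requires.
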